# 3 OBJECTIVES

The primary Phase II investigational objective is to show a differential effect on the pre-to-post-intervention change in upper extremity (UE) motor function between an interventional group receiving the MOVE-IT home exercise program (HEP) and a usual care treatment (UCT) group, as assessed by the Jebsen Taylor Hand Function Test (JTHFT) and other gold-standard clinical assessments of UE function.

Blinded assessors, certified for the study instruments, will evaluate children in both groups at pre-treatment (baseline), immediate post-treatment (baseline + 10 weeks), and 3 months post-treatment. Assessments (3 total) will take place in an outpatient setting and include the following blinded instruments:

- Jebsen Taylor Hand Function Test (JTHFT) (primary outcome measure)
- Quality of Upper Extremity Skills Test (QUEST) (dissociated movements and grasp components)
- Wolf Motor Function Test (WMFT)

Additionally, parents will be asked to complete the following parental report instrument during each assessment visit:

• Pediatric Motor Activity Log (inventory of child's functional use of the UE)

For both groups, parents will be asked to maintain a weekly activity log, including activities performed under the MOVE-IT intervention and any other therapy a child might receive.

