#### 4 STUDY DESIGN

The study is a randomized control study.

Following screening, enrolled subjects will be randomized to either the MOVE-IT home exercise program (HEP) or usual care treatment (UCT) group using a centralized and masked process developed by the study biostatistician. The HEP group is the interventional group. The UCT group is the control group. Following the control strategy previously adopted in the Children with Hemiparesis Arm and Movement Project (CHAMP) multi-site RCT (NICHD R01, trial registration number NCT01895660), children in the UCT group will be followed as they continue to receive their previously prescribed therapy services. As UCT group participants, these children will not receive any treatment services through the study. Parents will be asked to report therapy services their children receive during each assessment visit.

To ensure that an approximately equal number of subjects are randomized to the MOVE-IT HEP and UCT groups throughout the Phase II enrollment period, we will randomly assign the patients to the two study-groups in accordance with a permuted block randomization scheme. The randomization list will be generated by a UVA study biostatistician ([name]) using the PLAN procedure of SAS (SAS Institute Inc., Cary, NC). One subject randomization table will be generated for each site. The group assignment will be blinded to the therapists (raters) who perform the pre- and post-assessments. The group assignment will be not be blinded to the participants. The non-rater members of the IRB-approved study team will have access to the randomization list.

Demonstration of statistically significant improvement in UE motor function for participants the MOVE-IT HEP versus UCT will support the validity of MOVE-IT use as an intervention for children with hemiplegia. In home use, MOVE-IT will enable more frequent and intensive therapy with reduced travel and may extend the service range of existing rehabilitation providers to include underserved areas. In clinical practice, MOVE-IT will enable new models of delivery based on remote monitoring combined with outpatient services, increasing quality and efficiency of care. Statistical considerations for sample size determination, primary analysis, and secondary analyses are described below.

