#### Criteria for exclusion

- (1) History of uncontrolled seizures;
- (2) Has received botulinum toxin injections, stem cell infusions or another form of intensive UE therapy, such as CIMT, within the prior 6 months;
- (3) Unwillingness or inability to understand or follow verbal directions;
- (4) Diagnosis of moderate to severe cortical-visual impairment that in the judgement of the Principal Investigator could adversely impact the subject's participation;
- (5) Psychological diagnosis that in the determination of the Principal Investigator could significantly impact subject's participation or that could be aggravated by study participation;
- (6) Determination that participation would result in over exertion, or significant discomfort or pain;
- (7) Determination that participation would result in significant agitation or elevated stress;
- (8) Visual field deficit in either eye that impairs the ability to view the computer monitor.

Restrictions on use of other drugs or treatments: None

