# 6.2 Laboratory EvaluationsNo laboratory evaluations will be conducted under this study.

#### 7 STATISTICAL CONSIDERATIONS

#### 7.1 Study Outcome Measures

# 7.2 Sample Size Considerations

Power analysis for the study is based on approximate effect size and variance information derived from previous RCTs involving intensive therapy for children with hemiplegia. In particular, JTHF outcomes reported by Klingels et al. provide approximate effect size and variance. For the Wilcoxon Mann-Whitney test, if 20 subjects per group (40 total) complete the protocol, we will have at least 0.80 power ( $\alpha$ <0.05) if the true underlying probability that the MOVE-IT pre-to-post intervention change in JTHFT score is greater than the pre-to-post change for UCT is 0.75 or greater. Recruitment of 24 subjects per group will allow a conservative 15% dropout rate (e.g. compared to the CHAMP R01 program RCT, NCT01895660), which assumed 10%).

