## 7.3 Participant Enrollment and Follow-Up

Approximately 24 subjects will be recruited at each of the two sites (48 total). Recruited children will have a diagnosis of hemiplegia resulting from cerebral palsy, stroke, or other form of brain injury; be between 4 and 14 years of age; have no history of uncontrolled seizures; and be medically stable. Children will be excluded if they received botulinum toxin injections, stem cell infusions or another form of intensive UE therapy, such as CIMT, within the prior 6 months. Children may receive other forms of treatment or intervention during and after the MOVE-IT intervention; data about such other interventions will be collected prospectively from parents.

It is expected that participant enrollment in the MOVE-IT Phase II RCT will be open for a period of approximately 10 months. Monthly enrollment is projected to average from 6-12 new subjects per month across both sites. Each subject's participation includes a 10-week interventional (or control) period and a 3-month follow-up assessment.

An approximately equal number of subjects will be recruited at the UVA Children's Hospital (n=24) and the Duke Children's Hospital (n=24) study sites, facilitated by experienced study coordinators at each site. Based on recent completion of studies of similar scope, including the CHAMP CIMT trials at UVA [12], the team anticipates being able to meet the MOVE-IT RCT goals.

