#### 7.4 Analysis Plan

Primary variable analysis involves analysis of completion times for each of the seven tasks in the JTHFT which will be summed to produce a total score. The pre-intervention scores will be subtracted from the post-intervention scores to produce a set of delta values. These delta values scores ( $\Delta$ ) will be analyzed via Analysis of Covariance (ANCOVA). One null hypothesis will test if the mean pre-to-post-intervention change in the total JTHFT score is equal to zero, while the second null hypothesis will test if the mean pre-to post-intervention change in the JTHFT score is the same for patients who participate in a 10-week MOVE-IT HEP and patients who under UCT over the same duration. For both null hypotheses, a p $\leq$ 0.05 decision rule will be utilized as the rejection criterion. Analysis of data from the 3-month follow-up assessment will be performed in a similar manner.

Secondary variable analysis includes analysis of the pre-to-post intervention changes in the composite WMFT scores which will be analyzed in the same way as the pre-to-post intervention change in the composite JTHFT scores. The same method of analysis will be used to analyze the pre-to-post intervention changes in the QUEST scores.

The Likert scale responses to the SUS questionnaire will be summarized per question, and per question category, by frequencies and percentages. As an overall measure of system usability, a composite SUS score in the range from 0 to 100 will be derived from individual responses. By convention, a SUS score greater than or equal to 68 is indicative of an efficient, effective, and satisfying system. For the TAM questionnaire, percentages of favorable responses to the questions of each topic will be estimated via a binomial generalized estimating equation model, and a 90% confidence interval constructed. A Wald test will be used to test the null hypothesis that the odds of a favorable response are independent of the question topic.

Therapy session adherence and activity will be assessed by way of a binomial generalized estimating equation model, in which therapy adherence and activity measures (collected via parental logs) will be compared between the patients who participate in a 10-week MOVE-IT HEP and patients under UCT over the same duration.

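### Do the two JTHFT null hypotheses in Section 7.4, each tested at 0.05, leave open which test decides the trial?

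*Combined protocol and SAP*

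**What the plan says.** Section 7.4 sums the seven JTHFT task times, takes post minus pre, and analyses the differences by ANCOVA. It then sets two nulls. The first is stated as "One null hypothesis will test if the mean pre-to-post-intervention change in the total JTHFT score is equal to zero", with no arm named. The second is that HEP and UCT have the same mean change over the 10 weeks. For both, a p≤0.05 "decision rule will be utilized as the rejection criterion". The section gives no order, no adjustment, and no rule on whether one or both rejections are needed. It carries the approach forward: "Analysis of data from the 3-month follow-up assessment will be performed in a similar manner", and WMFT and QUEST, labelled secondary, are analysed in the same way.

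Three other parts of the same combined document bear on which test matters:

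- Section 3 (repeated in the Protocol Summary): "The primary Phase II investigational objective is to show a differential effect on the pre-to-post-intervention change" in motor function between the HEP and UCT groups.
- Section 4: "Demonstration of statistically significant improvement in UE motor function for participants the MOVE-IT HEP versus UCT will support the validity" of MOVE-IT. The same paragraph then points the reader to the statistical sections for the primary and secondary analyses.
- Section 7.2: power is stated for the probability that the "MOVE-IT pre-to-post intervention change in JTHFT score is greater than the pre-to-post change for UCT is 0.75 or greater".

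**The concern.** A test of change from zero has no control. Children aged 4 to 14 repeat a timed test, and both arms keep their prescribed therapy. Section 7.3 adds that "Children may receive other forms of treatment or intervention during and after the MOVE-IT intervention", and the exclusion criteria say "Restrictions on use of other drugs or treatments: None". Maturation, practice and background therapy could all move JTHFT times in both arms, and the first null could then be rejected with no MOVE-IT effect.

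The first null is also under-specified. HEP alone, UCT alone and all children are three different tests with different sample sizes.

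What would be at stake is the reading of a split result: change from zero significant, HEP versus UCT not. If that were reported as a positive trial, the protection given by randomization would be lost. If either rejection were enough for success, the 5% error rate would be exceeded even with no drift.

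**Working it through.** **Inputs from the plan.** 20 completers per group, 40 in total; power at least 0.80; P(MOVE-IT change exceeds UCT change) = 0.75; α = 0.05; 15% dropout; 24 recruited per group (Section 7.2). Two nulls, each at 0.05 (Section 7.4).

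**Assumptions.** Tests are two-sided. Change scores are normal with SD 1. The documents give no SD of JTHFT change and no expected drift, so drift common to both arms is taken as 0, 0.2, 0.3 and 0.5 SD.

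**Step 1: reproduce the plan's figure.** Noether's formula for the Wilcoxon Mann-Whitney test gives

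N = (1.960 + 0.842)² / (12 × 0.25 × (0.75 − 0.5)²) = 7.849 / 0.1875 = 41.9 in total.

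At N = 40, power = Φ(√(40 × 3) × 0.25 − 1.960) = Φ(0.779) = 0.78. Simulation under a normal shift giving P = 0.75 (0.954 SD) puts Wilcoxon power at 0.80 to 0.81. For dropout, 20 / 0.85 = 23.5, rounded up to 24. The stated figure therefore reproduces, and it concerns the HEP versus UCT comparison only. The change-from-zero test has no planned effect size and no stated power.

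**Step 2: error rate if HEP versus UCT decides.** With zero treatment effect, the simulated between-group rejection rate stays at 0.049 to 0.050 for drifts of 0.2, 0.3 and 0.5 SD. Common drift cancels in the difference.

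**Step 3: error rate if either rejection counted.** With zero drift and zero effect:

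- First null on all 40: the two tests are close to independent, so 1 − 0.95² = 0.0975.
- First null on HEP only: the tests are correlated, and simulation gives 0.049 + 0.051 − 0.016 = 0.084.

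If both rejections were required, the rate could not exceed 0.05.

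**Step 4: how often the first null is rejected under drift, with no treatment effect.**

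| Common drift (SD) | First null rejected, HEP n=20 | First null rejected, all n=40 | Split result, HEP | Split result, all 40 |
|---|---|---|---|---|
| 0.2 | 0.136 | 0.235 | 0.115 | 0.223 |
| 0.3 | 0.247 | 0.457 | 0.223 | 0.433 |
| 0.5 | 0.565 | 0.869 | 0.537 | 0.826 |

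A split result means the first null is rejected and the second is not. In the pooled case it is the rejection probability times about 0.95 (for example 0.869 × 0.95 = 0.826).

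These are not type I errors. Drift was put into the calculation, so the first null is false, and rejecting it is a correct statement about change over time.

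**Limit of the check.** The figures use t-tests on change scores because 7.4 names no covariates. With baseline as covariate, centred at its sample mean, and an assumed baseline-change correlation of −0.3, the change-from-zero test runs slightly above nominal size (about 0.055 in HEP, 0.060 in all 40), because sampling variation in the baseline mean is ignored. The between-group test was 0.051.

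**The case for a change.** The case for a change is that 7.4 is the section that fixes the tests, and it puts the two nulls on an equal footing. Intent stated elsewhere does not tell an analyst how to report a significant change from zero beside a non-significant group difference. Families are not blinded and the results go to publication, so a rule written before the data are seen is worth having. It would take one paragraph and leave N, data and power untouched.

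Much of this stands as a comment on drafting. Section 7.4 does not repeat the hierarchy, and the arm for the first null is unnamed. What does not stand is the step from there to a risk of a wrong conclusion. Protocol and SAP are one document, and Section 4 ties support for MOVE-IT to HEP versus UCT before directing the reader to the analyses. An author who claimed efficacy on the change-from-zero test alone would be departing from the stated objective, not using a freedom the plan grants.

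The carry-over to the 3-month, WMFT and QUEST analyses adds little. WMFT and QUEST are already called secondary, and no success claim is attached to the change-from-zero test in any of them. A test of change from zero is a legitimate supportive result; how prominently to show it is a matter of preference.

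**Conclusion.** The concern does not call for a change. Section 7.4 leaves a gap in wording that the objective, Section 4 and the power calculation already fill: HEP versus UCT in pre-to-post JTHFT change is the deciding comparison. Followed that way, the efficacy claim carries a type I error of 0.05 whatever the common drift, and 40 completers and 48 recruits stand as planned.

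The 0.084 to 0.098 figure depends on an either-null success rule that is not in the plan. The 0.136 to 0.869 range is power under an assumed drift, and the documents give no basis for preferring any value within it. An analyst can name the group when reporting the change-from-zero result and treat it as supportive without altering any planned test.

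This rests on two-sided testing and on reading the combined document as a whole. It would change only if the authors intended rejection of the first null alone to count as success, and nothing in the text says so.

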#### 5 STUDY POPULATION

#### 5.1 Selection of the Study Population

Ages: 4 - 14 years (inclusive)

Sex: Any Race: Any

Target # of subjects (at all sites) needed to complete protocol: 40.

Expected rate of screen failure/ dropouts/withdrawals from all sites: 15%.

Number of subject/dyads to be enrolled at all sites: 48.

Number of subjects who will sign a consent form under this protocol: 48 dyads.

(24 at UVA and 24 at Duke)

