#### ALL - Outpatient Visit 3: Follow-up Assessment (will last about 90 minutes)

- Conducted approximately 3 months after Post-Assessment.
- Blinded study therapist will administer the same battery of tests used in pre- and post-assessment.

To promote equipoise, parents of children in the UCT group will be provided free access to the MOVE-IT HEP following completion of the control protocol. When participation in the study is completed, all subjects will return to usual care under their individual health care provider.

A graphical summary of the MOVE-IT Phase II study is provided in Figure 2 below.

[figure not shown]

Figure 2. MOVE-IT Phase II Study Plan

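### As described, the 3-month JTHFT comparison makes no use of the recorded 10-week scores, and it can be biased if loss after Visit 2 depends on the 10-week result differently by arm

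*Combined protocol and SAP*

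**What the plan says.** Section 3 sets three assessments: "pre-treatment (baseline), immediate post-treatment (baseline + 10 weeks), and 3 months post-treatment". Section 6.1 places Visit 3 as follows: "Conducted approximately 3 months after Post-Assessment". It repeats the test battery there: "Blinded study therapist will administer the same battery of tests used in pre- and post-assessment". A child who attends Visit 2 but not Visit 3 will therefore normally have a 10-week JTHFT total on file.

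Section 7.4 sums the seven task times and forms one change per child: "The pre-intervention scores will be subtracted from the post-intervention scores to produce a set of delta values". These changes go into an ANCOVA whose covariates are not named. The follow-up visit gets one sentence: "Analysis of data from the 3-month follow-up assessment will be performed in a similar manner". WMFT and QUEST changes follow the same method.

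Section 7.4 gives no repeated-measures model for the motor outcomes, no imputation, no missing-data rule and no analysis set. Its only correlated-data models (GEE) are for the TAM questionnaire and for adherence. Loss is nevertheless expected. Section 7.2 bases power on the case "if 20 subjects per group (40 total) complete the protocol", out of 24 recruited per group. Section 5.1 gives "Expected rate of screen failure/ dropouts/withdrawals from all sites: 15" per cent, without a split by visit or arm.

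**The concern.** A 3-month change exists only for a child seen at Visit 3. An ANCOVA of those changes with baseline as covariate estimates the group difference without bias if, given baseline and arm, loss is unrelated to the outcome. A model of both visits together also copes with loss that depends on the recorded 10-week score.

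The weaker assumption matters here for three reasons:
- Section 4 leaves families unblinded.
- The two-weekly contacts in section 6.1 are described for the intervention period only.
- The reasons to return differ by arm. The MOVE-IT hardware is collected at the end of the home programme, while control families are offered access once they complete the control protocol.

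The 3-month comparison is the trial's only evidence on whether an effect lasts, and with 24 per arm the loss of two selected children can shift it.

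**Working it through.** **1. The plan's own figures.** Noether's formula, two-sided 0.05, 1:1, P = 0.75: N = (1.960 + 0.842)² / (12 × 0.25 × 0.25²) = 7.849 / 0.1875 = 41.9. At N = 40 the power is Φ(√(40 × 0.1875) − 1.960) = Φ(0.779) = 0.78. A simulated Wilcoxon-Mann-Whitney test under a normal shift gives 0.82. The stated 0.80 is reproduced. Enrolment also agrees: 20 / 0.85 = 23.5, rounded up to 24 per group. Going from 48 to 40 is a loss of 8/48 = 16.7%.

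**2. Assumptions, none given in the documents.**
- Baseline SD is 1, with normal scores.
- Correlation is 0.8 between baseline and each later visit, and 0.8 between the 10-week and 3-month residuals.
- Two children per arm are lost before Visit 2 and two more per arm before Visit 3.
- The true effect, where one is needed, is 0.60 SD. This follows from P = 0.75 only if r = 0.8: √2 × 0.6745 = 0.954 SDs of change; the SD of change is √(2 × 0.2) = 0.632; the product is 0.60. The documents plan no 3-month effect.

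Positive bias below means in favour of MOVE-IT.

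**3. Hand calculation.** Of 22 MOVE-IT children at Visit 2, suppose two are lost at random from the four with the poorest 10-week change.
- The lowest 4 of 22 standard normal values average −1.38.
- The remaining 20 therefore shift by 2 × 1.38 / 20 = 0.138 SDs of change.
- Given baseline, the 10-week residual has variance 1 − 0.64 = 0.36, so it shifts by 0.138 × 0.36 / 0.632 = 0.079.
- The 3-month residual shifts by 0.8 × 0.079 = **0.063 SD**.
- If two of the four best control responders are also lost, the bias doubles to 2 × 0.063 = **0.126 SD**.

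**4. Simulation, 3,000 to 4,000 trials per case, 3-month group difference.**

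| Loss after Visit 2 | Separate ANCOVA | Joint model |
|---|---|---|
| Random | no bias; power 0.85-0.86 | no bias; power 0.87-0.88 |
| Same rank-based rule in both arms | no bias | no bias |
| (b) Poor MOVE-IT responders | bias about 0.06 SD; type I error 6.2-6.7% | under 0.01 SD; 4.7-5.2% |
| (c) As (b), plus good control responders | bias 0.12-0.13 SD; type I error 9.7-11.5% | under 0.01 SD; 4.7-5.8% |

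The sampling SD of the estimate is about 0.19.

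**5. Milder versions (6,000 trials per case).**
- Loss follows a perception correlated 0.5 with the recorded change: (b) 0.032 SD, 5.4%; (c) 0.062 SD, 6.4%.
- One child per arm is lost after Visit 2, not two: (b) 0.030 SD, 5.0%; (c) 0.061 SD, 6.3%. By hand for (b): 1.38 / 21 × 0.36 / 0.632 × 0.8 = 0.030.

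**6. Other correlations and a logistic loss rule.** Loss after Visit 2 was set at 10% or 16.7%.
- (b): +0.04 to +0.08 SD at 10%; +0.07 to +0.14 SD at 16.7%.
- (c): +0.10 to +0.17 SD; +0.16 to +0.27 SD.
- Same rule in both arms, no effect: 0.
- Same rule in both arms, true 10-week effect 0.5-0.75 SD: −0.04 to −0.07 SD; −0.05 to −0.09 SD. More controls fall below the same absolute level of change, so more of them are lost, and the bias runs against MOVE-IT. A rank-based rule does not do this, because ranks within an arm ignore a shift.

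The joint model stayed within about 0.01 SD throughout.

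**The case against.** The strongest points on the other side are these.

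- **The primary result is not in question.** Objective and power concern the 10-week change. This stands. A reader might infer that the trial's main conclusion is at risk; the calculations do not support that.
- **Separate analyses are an inference.** Section 7.4 says only that the approach is similar. This also stands. The documented gap is the lack of any missing-data rule, and multiple imputation using the 10-week score would be another acceptable answer.
- **The adverse cases are severe.** Loss is picked from the extreme four of 22 on the recorded score. Nothing says families are told JTHFT results, so perceived progress is more realistic, and it roughly halves the bias.
- **Retention measures exist.** Section 5.3 pays $50 per outpatient visit. If completing the control protocol means attending Visit 3, the offer of MOVE-IT access works against the loss of control families in (c). On the other side, section 5.3 does not reimburse travel.
- **The loss split is a guess.** The 15% in section 5.1 also covers screen failures, so loss after Visit 2 may be smaller.
- **The simulated model is not exactly the proposed one.** The runs used maximum likelihood on normal data, not REML with Kenward-Roger, and summed completion times may be skewed. The joint model's near-zero bias follows from making loss depend on the recorded score.

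These points limit the size and certainty of the concern. They do not remove the gain: apart from simulation noise, the joint model was no worse than the ANCOVA in bias or type I error in any case run, and it gained slightly in power under random loss.

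**Conclusion.** The point holds in conditional form. On the natural reading of section 7.4, the 3-month comparison discards recorded 10-week information and can be biased when loss after Visit 2 depends on the 10-week result differently by arm. Under the stated assumptions the bias is about 0 with random loss or the same rank-based rule, about 0.06 SD with type I error of 6-7% in (b), and about 0.13 SD with 10-11% in the extreme case (c). It is roughly half that in the milder versions. Random loss costs about 2 power points at 3 months.

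Two stronger readings are tempting. One is that the 3-month result will be biased; the documents make arm-dependent loss plausible but do not show it. The other is that the bias favours MOVE-IT; with the same logistic rule in both arms and a true effect it ran the other way, at −0.04 to −0.09 SD. Nor should the bias be quoted as a share of a planned 3-month effect, since none is planned.

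**What to change.** In section 7.4, specify one likelihood-based repeated-measures model of the 10-week and 3-month JTHFT totals (or changes) in all randomised children, as assigned:
- terms for group, visit, group-by-visit and baseline total by visit, plus any covariates of the primary ANCOVA;
- unstructured covariance, REML and Kenward-Roger degrees of freedom;
- the 10-week group contrast as primary, and the 3-month contrast from the same fit;
- the separate ANCOVAs kept as sensitivity analyses.

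Do the same for WMFT and QUEST.

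The cost is SAP wording, a little programming and one extra covariance parameter, with no new data. The 10-week estimate barely changes. The model does not correct loss that depends on unobserved scores, and the text should say so. This is a cheap improvement, not a condition for the primary analysis to be valid.

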#### MOVE-IT HEP Home Visit 3 (will last about 90 minutes)

- At the end of the HEP period, a non-blinded team member will conduct a home visit at the patient's residence to recover the system hardware. Prior to recovery, a therapist will observe patients' independent use of the system either in the home or via an approved telehealth connection.
- Participants will respond to usability assessment instruments including:
  - System Usability Scale (SUS)
  - o Technology acceptance model (TAM) questionnaire
  - Short response open-ended narrative questions.

These assessments will be audio recorded using Zoom. The recordings will be stored in secure folders on O/drive at UVA and Duke Box, that only the research team has access to. The interview recording will only identify subjects with their subject ID. Transcriptions will be reviewed by a member of the research team for accuracy. Once reviewed and transcribed, all identifiable information will be removed and only the de-identified transcript will be stored and used for analysis. Another member of the research team will perform a quality check of the transcript to ensure accuracy.

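### The TAM topic comparison relies on a large-sample GEE Wald test in about 20-24 participants; run in the usual way, it rejects too often when several topics are tested jointly

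*Combined protocol and SAP*

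**What the plan says.** In Section 7.4 (Analysis Plan), the percentage of favorable TAM responses for each topic is to be "estimated via a binomial generalized estimating equation model, and a 90% confidence interval constructed". The next sentence sets the test: "A Wald test will be used to test the null hypothesis that the odds of a favorable response are independent of the question topic".

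The instrument appears in Section 6.1 under MOVE-IT HEP Home Visit 3, where "Participants will respond to usability assessment instruments including" introduces a list that contains the "Technology acceptance model (TAM) questionnaire". Nothing in the UCT procedures or in the assessment visits shared by both groups schedules it for controls.

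Section 7.2 gives the group size. Power is computed "if 20 subjects per group (40 total) complete the protocol", and "Recruitment of 24 subjects per group will allow a conservative 15% dropout rate".

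For the TAM analysis the plan does not give the number of topics, the items per topic, the working correlation, the variance estimator, the reference distribution, any small-sample correction or the significance level. The 0.05 rule in Section 7.4 is attached to the two JTHFT null hypotheses.

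**The concern.** The usual GEE Wald test combines an empirical sandwich variance with a chi-square reference, and both are justified only when there are many clusters. Here the cluster is the dyad, and there are 20-24 of them. In that range the sandwich variance tends to be too small and the chi-square reference ignores its sampling error. The effect grows with the number of topic contrasts tested together.

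At stake is a false statement that acceptance differs between topics. Section 8 says results go into NIH reports and publications, so a spurious difference could mislead readers about which aspects of the system families accept.

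**Working it through.** **Inputs from the plan.** Clusters K = 20 (completers) to 24 (enrolled) per group, Section 7.2. TAM in the HEP group only, Section 6.1. GEE, 90% interval and Wald test, Section 7.4.

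**Assumptions, because the plan is silent.** One respondent per dyad, complete data, 2-6 topics (T), empirical sandwich variance, chi-square and z references, test level 5%.

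**The plan's own figure.** The only sizing figure concerns the primary endpoint, and it is the source of K. Noether's formula for the Wilcoxon-Mann-Whitney test with N = 40 and P = 0.75 gives power Φ(√(12 × 40 × 0.25 × 0.25²) − 1.96) = 0.78. A simulation under a normal shift gives 0.81. Both are within 2 points of the stated 0.80. For dropout, 20/0.85 = 23.5, rounded up to 24. The plan states no size or power for the TAM test.

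**Size of the topic test, analytic approximation.** With q = T − 1 contrasts and an uncorrected sandwich (divisor K), the Wald statistic behaves approximately like a Hotelling statistic:

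W ≈ [Kq/(K − q)] × F(q, K − q)

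so the actual size is P{F(q, K − q) > c(K − q)/(Kq)}, where c is the 95% point of chi-square on q degrees of freedom. For K = 20 and T = 4: q = 3, c = 7.815, threshold 7.815 × 17/60 = 2.214, and P{F(3, 17) > 2.214} = 12.4%.

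**Size by simulation.** Logit topic model with sandwich variance, 6,000 runs per setting; 1, 3 or 5 items per topic; favorable rate 0.60, 0.75 or 0.90; latent within-person correlation 0.2 or 0.5. The table gives the median and range over settings with under 10% undefined fits.

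| Topics | K = 20, analytic | K = 20, simulated | K = 24, analytic | K = 24, simulated |
|---|---|---|---|---|
| 2 | 7.1% | 7.0% (4.4-8.5) | 6.8% | 6.4% (4.5-7.6) |
| 3 | 9.5% | 8.9% (5.3-12.6) | 8.6% | 8.0% (5.5-11.0) |
| 4 | 12.4% | 12.1% (6.9-18.8) | 10.9% | 10.1% (6.8-16.5) |
| 5 | 16.0% | 14.8% (9.7-28.9) | 13.7% | 12.9% (8.6-23.1) |
| 6 | 20.5% | 19.6% (13.2-38.7) | 17.1% | 16.6% (11.5-31.9) |

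**The 90% interval.** The same approximation gives coverage P{|t(K − 1)| < 1.645√((K − 1)/K)}. For K = 20 this is P{|t(19)| < 1.603} = 87.5%; for K = 24 it is P{|t(23)| < 1.610} = 87.9%. Simulated medians are 88.5-89.2%, with settings ranging from 85% to 94%.

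**Other variance choices** (exchangeable working correlation, 3 items per topic, 75% favorable, up to 600 runs per setting):
- Model-based variance with a chi-square reference: about 3-5% if the working correlation is right, 9-11% if it is wrong.
- Bias-corrected sandwich with a chi-square reference, K = 20: about 4-6% with 2 topics, 8-12% with 4, 15-18% with 6.

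**After the correction.** Referring the statistic to F(q, K − q) gives a median size of 4.3-4.8% for every number of topics. The worst settings (90% favorable, high correlation) still reach 6-19%. A t interval with variance factor K/(K − 1) has median coverage of about 91%.

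**Sparse topics.** With one item per topic and 90% favorable, 15-52% of simulated datasets have a topic at 0% or 100%, where the logit Wald test is undefined. Among the remaining datasets with 2-3 topics, the test is conservative (0.5-4%).

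**The case against.** The strongest reply is that the plan names neither a sandwich variance nor a chi-square reference. A GEE Wald statistic can be computed with a model-based or bias-corrected variance and referred to an F distribution, so this could be an unstated detail rather than an error. That stands in part: the inflation depends on how the test is run. But nothing in Section 7.4 prevents the usual version. Model-based variance is safe only if the working correlation is right, and the plan specifies none.

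A reader might go further in four ways that the documents do not support.
- **That the true type I error is well above 5%.** No number of topics and no level are stated. With 2 topics the excess is 1-2 points, and in sparse settings with few topics the test is conservative.
- **That the 90% interval is materially too narrow.** The typical shortfall is 1-3 points, and coverage exceeds 90% in some settings.
- **That the adherence GEE has the same problem.** That model compares both groups, so it has 40-48 clusters, and a simple group contrast has 1 degree of freedom. The size is about 6%, which is trivial.
- **That the trial's conclusions are at risk.** The TAM is a one-arm usability measure, absent from the objectives in Section 3, and no decision rule depends on the topic test.

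**Conclusion.** The concern holds in conditional form. With 20-24 clusters, an empirical sandwich variance, a chi-square reference and a 5% level, the topic test rejects a true null about 6-7% of the time with 2 topics, 10-12% with 4 and 17-21% with 6. The analytic approximation and the simulation agree closely for 2-4 topics and show the same trend for 5 and 6. The variance estimator, reference distribution, level and number of topics are all assumptions. The interval's typical coverage of 87-89% is a minor matter. The point is worth acting on because the plan makes this a formal hypothesis test and a better-calibrated one costs little. Efficacy is unaffected.

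**What to change.** Amend the TAM paragraph of Section 7.4 as follows.

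1. Refer the joint topic test to an F distribution with cluster-based denominator degrees of freedom, for example F(q, K − q), where q is the number of topics minus one and K the number of responding dyads.
2. Preferably add a bias-corrected sandwich variance (for example Kauermann-Carroll or Mancl-DeRouen). It does not replace step 1, because with a chi-square reference it leaves most of the inflation at 4 or more topics.
3. Use t rather than z quantiles for the 90% interval.
4. State the number of topics and the significance level.
5. Give a rule for topics with 0% or 100% favorable responses. The F reference alone does not repair sparse settings.

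The cost is a few sentences and a software option, slightly wider intervals and less power for the topic test. With t quantiles and a K/(K − 1) variance factor, intervals widen by about 8% at K = 20 (1.729 × √(20/19)/1.645 = 1.08) and 6% at K = 24 (1.714 × √(24/23)/1.645 = 1.06).
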